1.0 INTRODUCTION

1.1 Endometrial Cancer and Treatment

The incidence of endometrial cancer in the United States in 2008 was 40,100, with 7,470 deaths from this disease [1]. The majority of patients diagnosed with uterine cancer are diagnosed at an early stage (FIGO stage I), when surgical resection often leads to a good prognosis [2]. While hysterectomy and bilateral salpingo-oophorectomy are the standard of care for stage I tumors, the role for lymphadenectomy is still highly debated. This is due to the fact that there are significant risks associated with this procedure, including increased operative time and surgical complications, lymphedema, and lymphocyst formation [3]. Furthermore, evidence suggests that lymphadenectomy for stage I disease affords no improvement in overall or recurrence free survival [4]. Nonetheless, approximately 10% of women with stage I disease will have metastases to the pelvic lymph nodes, a finding which changes both the treatment recommendations and prognosis for the patient [5].

For this reason, SLN sampling is a surgical procedure that has gained enthusiasm as a means of identifying those patients who should be upstaged. This technique has been shown to be more accurate than MRI or CT scan [6], but without the risks associated with complete lymphadenectomy [7].

In higher risk disease (both higher stage as well as for tumors with intermediate risk factors), the role of SLN biopsy also remains unclear. While lymphadenectomy remains the standard of care in this patient population, SLN biopsy may be useful in patients who either refuse lymphadenectomy or for those patients who are unable to undergo this procedure due to surgical risk factors.

1.2 Sentinel Lymph Node Biopsy

The theory behind SLN biopsy is that the sentinel node is the first node in the lymphatic drainage pattern from a tumor; therefore, if this node is negative for metastasis, the remaining nodes should also be negative [8]. Techniques to identify the sentinel lymph node include injection of dye or radioisotope (most often into the tumor site), which then travels through the lymphatic system to the sentinel node. This node is then detected either by visualization (if dye is used) and/or by a gamma probe and specialized imaging (for radioisotope localization). Once the sentinel node has been identified, the node is removed and sent to pathology to be examined for evidence of metastases. Pathologists are now using advanced techniques such as ultrastaging and immunohistochemistry to help reveal micrometastases [9,10]. If metastases are noted, then a complete lymphadenectomy is carried out. If no metastasis is evident in the sentinel node, then further dissection is not necessary [11]. While the literature suggests that there is a learning curve for surgeons utilizing this technique, after approximately 30 cases [12,13], SLN biopsy can be performed with good and reliable results [11].

This concept was first described by Cabanas in 1977 [14]. Subsequently, significant work was done in both melanoma [15] and breast cancers [8], where sentinel lymph node biopsy, rather than complete lymphadenectomy, has become accepted as routine practice [16]. The approval of this technique in these cancers is based on significant evidence showing that the correct sentinel node from a tumor could be determined with high sensitivity and low false

negative rate [11]. This means that there must be few cases in which the sentinel node is negative, while a positive node went unidentified.

1.3 Sentinel Lymph Node Biopsy in Endometrial Cancer

Burke et al. first introduced SLN biopsy for endometrial cancer in 1996[17]; however this technique has only more recently begun further evaluation as of the 21st century. Kang et al performed a recent meta-analysis in 2011, which identified the current body of evidence available. Through an extensive literature search, this manuscript identified 26 studies on sentinel lymph node biopsy in endometrial cancer (see Table 1) [18].

Table 1. (from Kang et al.) [18] Meta-analysis of 26 studies

Authors	Year	N	Injection site	Route of surgery	Detection method	Pathology Assessment	Study
Burke et al.	1996	15	SM	Laparotomy	Dye only	HE	Unknown
Gargiulo et al.	2003	11	C	Laparoscopy	Both	HE/IHC	Unknown
Pelosi et al.	2003	16	C	Laparoscopy	Both	HE/IHC	Unknown
Petynski et al.	2003	33	SM/C	N/S	Both	N/A	Unknown
Fersis et al	2004	10	HS	Laparotomy	Isotope only	HE	Unknown
Houb et al.	2004	25	SM/C	Laparoscopy	Dye only	HE	Unknown
Lelievre et al.	2004	12	C	Laparotomy/scopy	Both	HE/IHC	Prospective
Niikura et al.	2004	28	HS	Laparotomy	Isotope only	HE/IHC	Unknown
Gien et al.	2005	16	HS	Laparotomy	Dye only	HE	Unknown
Maccauro et al.	2005	26	HS	Laparotomy	Both	HE/IHC	Unknown
Dzvincuk et al.	2006	33	C	Laparotomy/scopy	Isotope only	N/A	Prospective
Altgassen et al.	2007	23	SM	Laparotomy	Dye only	HE/IHC	Unknown
Dealoye et al.	2007	60	HS	Laparotomy/scopy	Both	HE/IHC	Unknown
Frumovitz et al.	2007	18	SM	Laparotomy	Both	HE	Prospective
Li et al.	2007	20	SM	Laparotomy	Dye only	HE	Unknown
Lopes et al.	2007	40	SM	Laparotomy	Dye only	HE/IHC	Unknown
Ballester e al.	2008	46	C	Laparotomy/scopy	Both	HE/IHC	Unknown
Bats et al.	2008	43	C	Laparotomy/scopy	Both	HE/IHC	Prospective
Perrone et al.	2008	40	HS, C	Laparoscopy	Isotope only	HE/IHC	Unknown
Robova et al.	2009	91	SM/H	Laparotomy	Both	HE	Prospective
Vidal-Sicart et al.	2009	35	N/A	N/A	Isotope only	N/A	Unknown
Zenzola et al.	2009	14	C	Laparotomy	Both	N/A	Unknown
Feranec et al.	2010	21	HS	Laparotomy	Both	N/A	Unknown
Mais et al.	2010	34	C	Laparotomy/scopy	Dye only	HE/IHC	Prospective
Ballester et al.	2011	125	C	Laparotomy/scopy	Both	HE/IHC	Prospective
Khoury-Collado et al.	2011	266	C, C/SM	Laparotomy/scopy	Dye only, both	HE/IHC	Prospective

N/A = not available; SM = subserosal myometrium; C = cervix; HS = hysteroscopic; HE = hematoxylin-eosin staining; IHC = immunohistochemistry.

This meta-analysis reported a detection rate of 78% and a sensitivity of 93% for sentinel lymph node biopsy. From this study, assuming a 10% metastasis risk, a false negative rate of 1% was calculated [18].

Since the publication of this meta-analysis, there have been four additional prospective studies on SLN biopsy in endometrial cancer that these authors were able to identify. Examining the results from these 4 prospective trials, sensitivity of SLN biopsy is high, and negative predictive value (NPV) is also relatively high (Table 2.).

Table 2. Results from recent prospective studies

Author	Year	Type	Pts	Detection	Inj	Procedure	Detection	Sens	NPV
How	2012	Prospective	100	Isotope	C	Robotic	92%	89%	99%
Solima	2012	Prospective	59	Isotope	H	Ex-lap or LSC	95%	90%	98%
Buda	2012	Prospective	25	Isotope/ISB	C	Ex-lap or LSC	91%	100%	Unk
Ballester	2011	Prospective	125	Isotope/ISB	C	Ex-lap or LSC	89%	84%	97%

While the evidence that exists is encouraging, it is important to recognize that we are still in the early stages of analysis of SLN biopsy in endometrial cancer. The number of patients studied thus far does not yet allow us to get an accurate sense of the true false-negative rate [3], and large, prospective, randomized controlled trials will be necessary to validate these findings.

1.4 Clinical Data-Techniques for Sentinel Lymph Node biopsy in Endometrial Cancer

While SLN biopsy appears to be a promising development in the treatment of endometrial cancer, several details regarding the techniques utilized must also be clarified. Two areas that remain controversial are the ideal site of injection, and the detection method utilized (dye versus isotope versus both isotope and dye, versus new techniques using ICG). To date, the studies that have been done have utilized a variety of these techniques, and it remains unclear which provide the most optimal results (Table 1).

1.4.1 Injection Site

Anatomically, the lymphatic drainage from the uterus is complex, with the lower uterine segment draining to the pelvic lymph nodes, and the upper segment draining to the para-aortic nodes. For this reason, injection site for SLN biopsy in endometrial cancer has been brought into question. Three sites of injection have been explored and reported: 1. uterine subserosa (7 studies with detection rates ranging from 0-92%), 2. cervix (7 studies [with or without additional injection into the myometrium] with detection rates ranging from 83-100%), and 3. endometrium, via hysteroscopy (5 studies with detection rates from 0-100%) [3]. While all 3 sites have shown high detection rates, there are several advantages to performing the injection into the cervix.

Although cervical and endometrial lymphatic spread patterns are different, deep injection into the cervix has demonstrated that the proper areas of drainage are reached [3], with good

penetration to the uterine vessels, parametria, lower uterine segment, and to the cornua [19], Accordingly, a recent meta-analysis showed that peri-cervical injection was associated with a statistically significant increase in detection rate of sentinel node when compared with other sites [18]. Additionally, injection into the cervix is technically advantageous as this is the easiest site to reach pre-operatively [3]. The trend in the literature is also toward cervical injection, with the 4 most recent prospective studies utilizing this technique (see Table 1).

1.4.2 Detection Method

Blue dye alone, radioisotope alone, or combinations of both detection methods have all been utilized in the literature (see Table 1), and while the optimal strategy remains unknown, each technique has advantages and disadvantages. The major disadvantages of isotope injection are that it must be performed on either the day before or the morning of surgery. Furthermore, this must be done in the nuclear medicine department, and it therefore requires extensive logistical coordination and preparation in order to optimize results [20]. This technique can therefore be technically challenging as well as costly. The injection of dye is much simpler, as it is injected immediately prior to surgery, and additional dye can be injected if needed [19]. It is additionally less costly. While allergic reactions to dye are rare (<1%) and often mild, severe allergic reactions have been reported [19].

The evidence for the optimal technique is inconsistent, with some evidence suggesting that the detection rates are equivalent and some suggesting that the combination of isotope and blue dye injection is superior [7]. However, due to the logistical challenges and cost associated with isotope injection, the cost-benefit of adding this technique is unclear. Furthermore, evidence from gynecologic oncology literature suggests a similar learning curve for SLN biopsy, with approximately 30 cases as the plateau point [10]. Some evidence suggests that experience of the surgeon rather than detection method is the more critical factor in the detection rate [18].

[figure not shown]
New detection methods and techniques are also currently being investigated, such as the use of fluorescing dye. While further studies are needed to compare these methods to conventional blue dye and isotopes, studies that have utilized ICG in other sites are very promising. ICG is a tricarbo-cyanine dye that fluoresces in the near infrared spectrum when illuminated with 806nm light. The fluorescent light is then captured with a special video camera device that allows the ICG to be displayed in the visible light spectrum. ICG is highly water-soluble and rapidly binds to plasma proteins, qualities that make it useful for assessment of blood flow [21]. Therefore, it has been used surgically to assess patency of grafts in vascular surgery [22], coronary artery bypass grafting [21], transplant surgery and plastic surgery procedures that require flap reconstruction [23]. Because ICG binds to albumin and therefore has a propensity for lymphatic tissue, in the early 2000's, it was first hypothesized that ICG might be a useful injectant for sentinel node identification. In 2005, Kitai et al investigated the use of ICG for SLN biopsy in breast cancer and were the first to propose that the use of ICG could improve both detection rate and negative predictive value of SLN biopsy in breast cancer [24]. This technique has become more popular, particularly for SLN biopsy in breast cancer [25] and melanoma, and recent data suggests that the lymphatic drainage pattern of ICG is identical to that of radioisotope [26]. There are only 2 studies that have utilized ICG for sentinel node detection in endometrial cancer. The first study found that ICG was superior to isosulfan blue for SLN detection and that by using a

combination of ICG and isosulfan blue, a 100% detection rate could be achieved [27]. The other study was a feasibility study for sentinel lymph node biopsy utilizing robotics in both endometrial and cervical cancer patients. This study showed a comparable detection rate to isotope and blue dye in a small sample [28].

1.4.3 An Algorithm for Sentinel Lymph Node Biopsy

In a recent report by Barlin et al., the use of a sentinel lymph node mapping algorithm for endometrial cancer was introduced. These authors propose that by following this algorithm, the false-negative rate for SLN biopsy can be minimized. This algorithm is as follows: evaluation of the peritoneum and serosa via washings, evaluation of the retroperitoneal lymph nodes via mapping for the SLN and removal of any suspicious node. If there is no mapping to a hemi-pelvis, a complete pelvic lymphadenectomy should be performed on that side. Para-aortic lymphadenectomy should be performed at the discretion of the surgeon (please see Figure 1). Utilizing this algorithm may help to further diminish the false-negative rate of SLN biopsy, even in more high risk stage I endometrial cancers [29].

Figure 1. (From Barlin et al. [29]) Surgical algorithm for endometrial cancer

1.4.4 Surgical Modality and Sentinel Lymph Node Biopsy

To our knowledge, thus far, sentinel lymph node biopsy procedures have been performed by laparotomy, conventional laparoscopy, and conventional robotics. Evidence suggests that minimally invasive techniques, including laparoscopy and robotics, should now be the standard of care for endometrial cancer [30], however, at times, open procedures may also be

necessary. Single-port laparoscopy is also now being utilized for endometrial cancer cases [31], yet, to our knowledge, there are no reports of single-port technology utilized for sentinel lymph node biopsy. While there is still limited prospective data on the benefits of single-port techniques, the available data suggests that outcomes for single-port laparoscopy are similar to those of conventional laparoscopy, with the added benefit of improved cosmesis and decreased pain [32].

The most recent advance in single-port technology is the single-port robot, which is now FDA-approved for gynecologic cases [33]. Robotic technology has provided improved optics, improved range of motion, and a shorter learning curve when compared to conventional laparoscopy [34]. A recent study by Escobar et al. compared LESS surgery to conventional LSC and robotic surgery for endometrial cancer and found no difference in outcomes [35]. In a recent study by Rossi et al, the robot was utilized to perform SLN biopsy in both endometrial and cervical cancers. The findings in this study suggest that robotics might have additional advantages specific for SLN biopsy procedure. This study showed a relatively short operating room time (186 min from patient entry into the room until exiting the room), as well as the ability to utilize new and integrated technologies (a fluorescence imager) [28]. These advantages will also translate to single-port robotics as technology develops [31].

1.5. **Rationale**

By performing sentinel lymph node biopsy for endometrial cancer, we may be able to further minimize the risks of lymph node evaluation, while continuing to obtain critical prognostic information for patients. In this study, we examine detection rates, false negative rates, and negative predictive value of SLN biopsy for endometrial cancer in order to further add to the body of evidence on SLN biopsy for endometrial cancer.

2.0 OBJECTIVES

2.1 Primary Objective

To determine the detection rate, sensitivity, and negative predictive value of SLN biopsy in endometrial cancer patients.

2.2 Secondary Objective(s)

To compare different surgical modalities (open procedures, minimally invasive procedures, and single-site technology) and different injectants (isosulfan blue and indocyanine green) for SLN biopsy.

To determine total operating room time (from the time the patient enters the room to the time the patient leaves the room) as well as console time (robotic)/ operating time for minimally invasive procedures.

3.0 STUDY DESIGN

3.1 Study design

This is a prospective cohort analysis. Consecutive, eligible, consenting patients will be enrolled into the study, and data will be collected on their operative procedure and pathology.

3.2 Number of Subjects

For this study, a sample size of 200 patients will initially be included. This sample size was calculated using the Raosoft sample size calculator online (available at <http://www.raosoft.com/samplesize.html>). A 5% margin of error was used, with a 95% confidence interval, a population size of 20,000 (as suggested), and a 15% response distribution. This 15% response distribution was chosen based on 2 large randomized trials that showed that the rates of positive pelvic lymph nodes in patients with presumed stage I-II disease were 9% and 13% respectively [36, 37]. In order to ensure an adequate sample size a 15% difference was utilized for this calculation.

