10.1.1 Definitions

Sensitivity, false negative and false negative rate will be limited to those patients in whom a sentinel node is detected.

False negative = a sentinel node that is identified and determined to be negative, however, upon complete lymphadenectomy, a different lymph node is found to be positive

Sensitivity = the number of patients with a positive SLN over those patients with a positive SLN plus those patients with a false negative lymph node

False negative rate = 1-sensitivity or the number of patients with a false negative SLN over the number of patients with a positive SLN plus those with a false negative lymph node

	Our definition	Other definition
FN	H	F+H
FN Rate	$H/D+H$	$F+H/D+F+H$
Sensitivity	$D/D+H$	$D/D+F+H$
NPV	I/E	-

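### The 5% margin behind the 200 patients belongs to node positivity, which is not an endpoint; the precision of sensitivity and the false negative rate is unstated and would be about 11 to 21 points.

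*Combined protocol and SAP*

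**What the plan says.** Section 3.2 states that "a sample size of 200 patients will initially be included". The inputs to the online survey calculator were these: "A 5% margin of error was used, with a 95% confidence interval, a population size of 20,000 (as suggested), and a 15% response distribution". The 15% is explained by two randomized trials in which the "rates of positive pelvic lymph nodes in patients with presumed stage I-II disease were 9% and 13% respectively", rounded up for safety.

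The primary objective in Section 2.1 is different: "To determine the detection rate, sensitivity, and negative predictive value of SLN biopsy in endometrial cancer patients". Section 10.1.1 then narrows two of the measures: "Sensitivity, false negative and false negative rate will be limited to those patients in whom a sentinel node is detected". It defines sensitivity as patients with a positive sentinel node divided by those patients plus the false negatives, and the false negative rate as one minus sensitivity.

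Section 1.3 says of the earlier evidence: "The number of patients studied thus far does not yet allow us to get an accurate sense of the true false-negative rate". Section 1.5 says this study examines that rate. Section 10.1 evaluates success by detection rate, sensitivity and false negative rate. It cites a breast cancer guideline (detection 85%, false negative rate at most 5%) and reported false negative rates of 4.7% to 9.8% in breast cancer and about 7.7% to 8.3% in vulvar cancer. Section 12.0 promises 95% confidence intervals for sensitivity, specificity and NPV but sets no target width.

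**The concern.** The only precision figure behind the sample size is attached to a quantity that is not an endpoint. A reader of Section 3.2 could take it that 200 patients give about 5 points on the primary measures. For sensitivity that cannot be so, because its denominator is the small group of mapped, node-positive women and not all 200.

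The false negative rate is the quantity the introduction says is poorly known, and it is one of the measures of success. If the expected interval is so wide that it covers both the guideline limit and all the comparator rates, the plan should say so before enrolment, so that a low observed rate is not read as meeting the benchmark. Section 3.2 also says 200 will be included initially but gives no rule for extending.

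**Working it through.** **1. The plan's figure.** With z = 1.96, p = 0.15 and E = 0.05:
- z²p(1−p)/E² = 195.9; with a finite population of 20,000 it is 194.0.
- At n = 200 the margin is 1.96 × √(0.15 × 0.85/200) = 4.95 points.

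So 200 reproduces as a rounded-up figure, and the margin is that of node positivity.

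**2. Denominator for sensitivity.** Inputs:
- Node positivity 9% and 13%, and the planning value 15% (Section 3.2).
- Detection: "This meta-analysis reported a detection rate of 78% and a sensitivity of 93% for sentinel lymph node biopsy" (Section 1.3), up to the report that with a "combination of ICG and isosulfan blue, a 100% detection rate could be achieved" (Section 1.4.2).
- Sensitivity 84% (lowest in Table 2) to 93% (the meta-analysis).

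Mapped node-positive women = 200 × positivity × detection, taking detection as unrelated to nodal status and assuming every mapped patient has the complete lymphadenectomy:
- 200 × 0.09 × 0.78 = 14.0
- 200 × 0.13 × 1.00 = 26.0
- 200 × 0.15 × 1.00 = 30.0

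**3. Exact (Clopper-Pearson) 95% intervals for sensitivity**, at the nearest whole count, with half-width = (upper − lower)/2:

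| Observed | 95% interval | Half-width (points) |
|---|---|---|
| 12/14 | 57.2% to 98.2% | 20.5 |
| 13/14 | 66.1% to 99.8% | 16.8 |
| 22/26 | 65.1% to 95.6% | 15.3 |
| 24/26 | 74.9% to 99.1% | 12.1 |
| 25/30 | 65.3% to 94.4% | 14.5 |
| 28/30 | 77.9% to 99.2% | 10.6 |

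Over every n from 14 to 30 at 84% to 93% sensitivity, the half-width runs from 10.6 (28/30) to 20.8 (13/16). Wilson intervals give 9.7 to 18.2. The false negative rate has the same widths, being the complement.

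**4. What can be said against the 5% benchmark.**
- With no false negatives the upper limit is 1 − 0.025^(1/n): 23.2% (n = 14), 13.2% (n = 26), 11.6% (n = 30). An upper limit of 5% or less needs 72 such women with none.
- With 0 to 3 false negatives, the interval contains the whole range 4.7% to 9.8% at every n from 14 to 30. The closest case is 3/14, with a lower limit of 4.66%.
- The lower limit exceeds 5% only with at least 4 false negatives (n = 14 to 22) or 5 (n = 23 to 30). Examples: 4/14 gives 8.4% to 58.1%; 5/30 gives 5.6% to 34.7%.
- The binomial chance of reaching that count is 17% (n = 14) to 54% (n = 30) if true sensitivity is 84%. If it is 93%, the chance is 1.4% (n = 14) to at most 6.4% (n = 22).

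**5. The other primary endpoints at 200 patients, exact half-widths.**
- Detection rate: 3.3 points at 190/200 (95%), 5.2 at 170/200 (85%), 6.0 at 156/200 (78%).
- NPV: sentinel-negative women = mapped × (1 − positivity × sensitivity). This runs from 156 × (1 − 0.15 × 0.93) = 134 to 200 × (1 − 0.09 × 0.84) = 185. Half-widths run from about 1.5 points (1 false negative of 182) to 3.3 (4 of 136).

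**6. Higher positivity.** The eligibility criteria set no stage limit. Assuming every patient is mapped, and sensitivity again 84% to 93%, 20% positivity (n = 40) gives 9.4 to 12.1 points and 30% (n = 60) gives 7.2 to 10.1.

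**The case against.** Section 3.2 hides nothing: it says openly that the 15% comes from nodal positivity, and it never claims a 5-point margin for sensitivity. Because p(1−p) is the same at 15% and 85%, the same calculation happens to suit a detection rate of 85%, which is the cited benchmark, and NPV is estimated more tightly still. Section 12.0 commits to confidence intervals, so the uncertainty will be visible in the report. Section 10.1 sets no hypothesis or pass/fail rule for the false negative rate, so confirmation of 5% was never formally planned.

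Most of this stands, and it is why the number 200 need not change. It does not supply what is missing. Section 3.2 makes no link to detection rate, intervals in the final report are not a planning statement, and Section 10.1 does name success measures and a comparator.

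The range of 11 to 21 points is conditional. One 25-patient study in Table 2 reported 100% sensitivity; an observed 100% here would give 11.6 (14/14), 6.6 (26/26) or 5.8 (30/30) points. The upper count of 30 needs full mapping; with Table 2 detection of 89% to 95% the count is about 16 (200 × 0.09 × 0.89) to 29 (200 × 0.15 × 0.95). Conversely, Appendix A speaks of possible lymphadenectomy and Section 6.2 lets the surgeon vary the procedure, so the usable count could be lower. These points move the figure but do not bring it to 5 points at the protocol's positivity rates.

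**Conclusion.** The concern holds. The arithmetic behind 200 is sound but is applied to node positivity, and no precision is given for any primary endpoint. For detection rate and NPV the omission is mild. For sensitivity and the false negative rate, the expected exact 95% half-width is about 11 to 21 points, two to four times the 5 points quoted. This rests on 9% to 15% positivity, 78% to 100% detection, 84% to 93% sensitivity and complete lymphadenectomy in every mapped patient. On the same positivity and detection rates the study cannot confirm a false negative rate of 5% or less, even with a perfect result. It could show a rate above 5% if false negatives are frequent. The cohort remains valid; its sample-size statement should be corrected.

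**What to change.** Keep 200. In Section 3.2, say that the 5% margin and the 15% rate refer to node positivity, and add a statement such as:

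> Expected half-widths of exact (Clopper-Pearson) 95% confidence intervals with 200 patients, assuming 9–15% node positivity, 78–100% detection, 84–93% sensitivity and complete pelvic lymphadenectomy in all mapped patients: detection rate about 3.3 points at 95%, 5.2 at 85% and 6.0 at 78% detection; NPV about 1.5 to 3.3 points (134–185 women with a negative sentinel node); sensitivity and false negative rate about 11 to 21 points (14–30 node-positive women with a detected sentinel node).

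In Section 10.1, state that the comparison with the 5% benchmark and with the breast and vulvar rates is descriptive and is reported with the exact 95% interval. Add that it cannot confirm a false negative rate of 5% or less at the expected number of node-positive women, although it may show a higher one. If enrolment beyond 200 is intended, give the rule; otherwise drop the word initially.

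The cost is protocol wording: no extra patients and no change to the analysis. The stated precision for sensitivity becomes less favourable.
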